9.0 Ancillary Treatment/Supportive Care**9.1 Full supportive care**

Patients should receive full supportive care while on this study. This includes blood product support, antibiotic treatment, and treatment of other newly diagnosed or concurrent medical conditions. All blood products and concomitant medications such as antidiarrheals, analgesics, and/or antiemetics received from the first day of study treatment administration until 30 days after the final dose will be recorded in the medical records.

9.2 Blood products and growth factors

Blood products and growth factors should be utilized as clinically warranted and following institutional policies and recommendations. The use of growth factors should follow published guidelines of the Journal of Clinical Oncology, Volume 33, No 28 (October 1), 2015: pp. 3199-3212 (WBC growth factors) AND Journal of Clinical Oncology, Volume 28, No 33 (November 20), 2010: pp. 4955-5010 (darbepoetin/epoetin).

9.3 Antiemetics

Antiemetics may be used at the discretion of the attending physician.

9.4 Diarrhea

Diarrhea could be managed conservatively with loperamide. The recommended dose of loperamide is 4 mg at first onset, followed by 2 mg every 2-4 hours until diarrhea free (maximum 16 mg/day).

In the event of Grade 3 or 4 diarrhea, the following supportive measures are allowed: hydration, octreotide, and antidiarrheals.

If diarrhea is severe (requiring intravenous rehydration) and/or associated with fever or severe neutropenia (grade 3 or 4), broad-spectrum antibiotics must be prescribed. Patients with severe diarrhea or any diarrhea associated with severe nausea or vomiting **should be hospitalized** for intravenous hydration and correction of electrolyte imbalances.

10.0 Adverse Event (AE) Monitoring and Reporting

The site principal investigator is responsible for reporting any/all serious adverse events to the sponsor as described within the protocol, regardless of attribution to study agent or treatment procedure.

The sponsor/sponsor-investigator is responsible for notifying FDA and all participating investigators in a written safety report of any of the following:

- Any suspected adverse reaction that is both serious and unexpected.
- Any findings from laboratory animal or *in vitro* testing that suggest a significant risk for human subjects, including reports of mutagenicity, teratogenicity, or carcinogenicity.
- Any findings from epidemiological studies, pooled analysis of multiple studies, or clinical studies, whether or not conducted under an IND and whether or not conducted by the sponsor, that suggest a significant risk in humans exposed to the drug
- Any clinically important increase in the rate of a serious suspected adverse reaction over the rate stated in the protocol or Investigator's Brochure (IB).

Summary of SAE Reporting for this study
(please read entire section for specific instructions):

WHO:	WHAT form:	WHERE to send:
All sites	Pregnancy Reporting http://ctep.cancer.gov/protocolDevelopment/electronic_applications/docs/PregnancyReportFormUpdated.pdf	Mayo Sites – attach to MCCC Electronic SAE Reporting Form and submit to [REDACTED]
Mayo Clinic Sites	Mayo Clinic Cancer Center SAE Reporting Form http://livelcycle2.mayo.edu/workspace/?startEndpoint=MC4158-56/Processes/MC4158-56-Process.MC4158-56 AND attach MedWatch 3500A: http://www.fda.gov/downloads/AboutFDA/ReportsManualsForms/Forms/UCM048334.pdf	Submit to [REDACTED] Will automatically be sent to [REDACTED]

Definitions

Adverse Event

Any untoward medical occurrence associated with the use of a drug in humans, whether or not considered drug related.

Suspected Adverse Reaction

Any adverse event for which there is a reasonable possibility that the drug caused the adverse event.

Expedited Reporting

Events reported to sponsor within 24 hours, 5 days or 10 days of study team becoming aware of the event.

Routine Reporting

Events reported to sponsor via case report forms

Events of Interest

Events that would not typically be considered to meet the criteria for expedited reporting, but that for a specific protocol are being reported via expedited means in order to facilitate the review of safety data (may be requested by the FDA or the sponsor).

Unanticipated Adverse Device Event (UADE)

Any serious adverse effect on health or safety or any life-threatening problem or death caused by, or associated with, a device, if that effect, problem, or death was not previously identified in nature, severity, or degree of incidence in the investigational plan or application (including a supplementary plan or application), or any other unanticipated serious problem associated with a device that relates to the rights, safety, or welfare of subjects

10.1 Adverse Event Characteristics

CTCAE term (AE description) and grade: The descriptions and grading scales found in the revised NCI Common Terminology Criteria for Adverse Events (CTCAE) version 4.0 will be utilized for AE reporting. All appropriate treatment areas should have access to a copy of the CTCAE version 4.0. A copy of the CTCAE version 4.0 can be downloaded from the CTEP web site:

(http://ctep.cancer.gov/protocolDevelopment/electronic_applications/ctc.htm)

- a. Identify the grade and severity of the event using the CTCAE version 4.0.
- b. Determine whether the event is expected or unexpected (see Section 10.2).
- c. Determine if the adverse event is related to the study intervention (agent, treatment or procedure) (see Section 10.3).
- d. Determine whether the event must be reported as an expedited report. If yes, determine the timeframe/mechanism (see Section 10.4).
- e. Determine if other reporting is required (see Section 10.5).
- f. Note: All AEs reported via expedited mechanisms must also be reported via the routine data reporting mechanisms defined by the protocol (see Sections 10.6 and 18.0).

NOTE: A severe AE is NOT the same as a serious AE, which is defined in Section 10.4.

10.2 Expected vs. Unexpected Events

Expected events - are those described within the Section 15.0 of the protocol, the study specific consent form, package insert (if applicable), and/or the investigator brochure.

Unexpected adverse events or suspected adverse reactions are those not listed in Section 15.0 of the protocol, the study specific consent form, package insert (if applicable), or in the investigator brochure (or are not listed at the specificity or severity that has been observed); if an investigator brochure is not required or available, is not consistent with the risk information described in the general investigational plan.

Unexpected also refers to adverse events or suspected adverse reactions that are mentioned in the investigator brochure as occurring with a class of drugs but have not been observed with the drug under investigation.

An investigational agent/intervention might exacerbate the expected AEs associated with a commercial agent. Therefore, if an expected AE (for the commercial agent) occurs with a higher degree of severity or specificity, expedited reporting is required.

NOTE: *The consent form may contain study specific information at the discretion of the Principal Investigator; it is possible that this information may NOT be included in the protocol or the investigator brochure. Refer to protocol or IB for reporting needs.

10.3 Attribution to agent(s) or procedure

When assessing whether an adverse event (AE) is related to a medical agent(s) medical or procedure, the following attribution categories are utilized:

- Definite - The AE is *clearly related* to the agent(s)/procedure.
- Probable - The AE is *likely related* to the agent(s)/procedure.
- Possible - The AE *may be related* to the agent(s)/procedure.
- Unlikely - The AE is *doubtfully related* to the agent(s)/procedure.
- Unrelated - The AE is *clearly NOT related* to the agent(s)/procedure.

10.31 AEs Experienced Utilizing Investigational Agents / Commercial Agent(s)

NOTE: When a commercial agent(s) is (are) used on the same treatment arm as the investigational agent/intervention (also, investigational drug, biologic, cellular product, or other investigational therapy under an IND), the **entire combination (arm) is then considered an investigational intervention for reporting.**

- An AE that occurs on a combination study must be assessed in accordance with the guidelines for **investigational** agents/interventions.
- An AE that occurs prior to administration of the investigational agent/intervention must be assessed as specified in the protocol. In general, only Grade 4 and 5 AEs that are unexpected with at least possible attribution to the commercial agent require an expedited report, unless hospitalization is required. Refer to Section 10.4 for specific AE reporting requirements or exceptions.

An investigational agent/intervention might exacerbate the expected AEs associated with a commercial agent. Therefore, if an expected AE (for the commercial agent) occurs with a higher degree of severity or specificity, expedited reporting is required.

- An increased incidence of an expected adverse event (AE) is based on the patients treated for this study at their site. A list of known/expected AEs is reported in the package insert or the literature, including AEs resulting from a drug overdose.
- Commercial agent expedited reports must be submitted to the FDA via MedWatch 3500A for Health Professionals (complete all three pages of the form).

<http://www.fda.gov/downloads/AboutFDA/ReportsManualsForms/Forms/UCM048334.pdf>

or

<http://www.fda.gov/AboutFDA/ReportsManualsForms/Forms/ListFormsAlphabetically/default.htm>

Instructions for completing the MedWatch 3500A:

<http://www.fda.gov/downloads/Safety/MedWatch/HowToReport/DownloadForms/UCM387002.pdf>

10.32 EXPECTED Serious Adverse Events: Protocol Specific Exceptions to Expedited Reporting

For this protocol only, the following Adverse Events/Grades are expected to occur within this population and do not require Expedited Reporting. These events must still be reported via Routine Reporting (see Section 10.6).*

*Report any clinically important increase in the rate of a serious suspected adverse reaction (at your study site) over that which is listed in the protocol or investigator brochure as an expedited event.

*Report an expected event that is greater in severity or specificity than expected as an expedited event.

CTCAE System Organ Class (SOC)	Adverse event/ Symptoms	CTCAE Grade at which the event will not be reported in an expedited manner ¹
General disorders and administrations site conditions	Fatigue	≤Grade 3
	Malaise	≤Grade 3
Gastrointestinal disorders	Nausea	≤Grade 3
	Vomiting	≤Grade 3
	Diarrhea	≤Grade 3
Blood and lymphatic system disorders	Anemia	≤Grade 4
Investigations	Lymphocyte count decreased	≤Grade 4
	Neutrophil count decreased	≤Grade 4
	Platelet count decreased	≤Grade 4
	White blood cell count decreased	≤Grade 4

These exceptions only apply if the adverse event does not result in hospitalization. If the adverse event results in hospitalization, then the standard expedited adverse events reporting requirements must be followed.

Specific protocol exceptions to expedited reporting should be reported expeditiously by investigators **ONLY** if they exceed the expected grade of the event.

The following hospitalizations are not considered to be SAEs because there is no “adverse event” (*i.e.*, there is no untoward medical occurrence) associated with the hospitalization:

- Hospitalizations for respite care
- Planned hospitalizations required by the protocol
- Hospitalization planned before informed consent (where the condition requiring the hospitalization has not changed post study drug administration)
- Hospitalization for elective procedures unrelated to the current disease and/or treatment on this trial
- Hospitalization for administration of study drug or insertion of access for administration of study drug
- Hospitalization for routine maintenance of a device (*e.g.*, battery replacement) that was in place before study entry
- Hospitalization, or other serious outcomes for signs and symptoms of progression of the cancer.]

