10.4 Expedited Reporting Requirements for IND/IDE Agents

10.41 Phase 1 and Early Phase 2 Studies: Expedited Reporting Requirements for Adverse Events that Occur on Studies under an IND/IDE within 30 Days of the Last Administration of the Investigational Agent/Intervention ^{1,2}

FDA REPORTING REQUIREMENTS FOR SERIOUS ADVERSE EVENTS (21 CFR Part 312)

NOTE: Investigators **MUST** immediately report to the sponsor **ANY** Serious Adverse Events, whether or not they are considered related to the investigational agent(s)/intervention (21 CFR 312.64)

An adverse event is considered serious if it results in **ANY** of the following outcomes:

- 1) Death
- 2) A life-threatening adverse event
- 3) An adverse event that results in inpatient hospitalization or prolongation of existing hospitalization for ≥ 24 hours
- 4) A persistent or significant incapacity or substantial disruption of the ability to conduct normal life functions
- 5) A congenital anomaly/birth defect.
- 6) Important Medical Events (IME) that may not result in death, be life threatening, or require hospitalization may be considered serious when, based upon medical judgment, they may jeopardize the patient or subject and may require medical or surgical intervention to prevent one of the outcomes listed in this definition. (FDA, 21 CFR 312.32; ICH E2A and ICH E6).

ALL SERIOUS adverse events that meet the above criteria **MUST** be immediately reported to the sponsor within the timeframes detailed in the table below.

Hospitalization	Grade 1 and Grade 2 Timeframes	Grade 3-5 Timeframes
Resulting in Hospitalization ≥24 hrs	7 Calendar Days	24-Hour 3 Calendar Days
Not resulting in Hospitalization ≥24 hrs	Not required	

Expedited AE reporting timelines are defined as:

- "24-Hour; 3 Calendar Days" - The AE must initially be reported within 24 hours of learning of the AE, followed by a complete expedited report within 3 calendar days of the initial 24-hour report.
- "7 Calendar Days" - A complete expedited report on the AE must be submitted within 7 calendar days of learning of the AE.

¹Serious adverse events that occur more than 30 days after the last administration of investigational agent/intervention and have an attribution of possible, probable, or definite require reporting as follows:

Expedited 24-hour notification followed by complete report within 3 calendar days for:

- All Grade 3, 4, and Grade 5 AEs

Expedited 7 calendar day reports for:

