10.52 Death

Note: A death on study requires both routine and expedited reporting regardless of causality, unless as noted below. Attribution to treatment or other cause must be provided.

Any death occurring within 30 days of the last dose, regardless of attribution to an agent/intervention under an IND/IDE requires expedited reporting within 24-hours.

Any death occurring greater than 30 days with an attribution of possible, probable, or definite to an agent/intervention under an IND/IDE requires expedited reporting within 24-hours.

Reportable categories of Death

- Death attributable to a CTCAE term.
- Death Neonatal: A disorder characterized by cessation of life during the first 28 days of life.
- Death NOS: A cessation of life that cannot be attributed to a CTCAE term associated with Grade 5.
- Sudden death NOS: A sudden (defined as instant or within one hour of the onset of symptoms) or an unobserved cessation of life that cannot be attributed to a CTCAE term associated with Grade 5.
- Death due to progressive disease should be reported as **Grade 5 “Neoplasms benign, malignant and unspecified (including cysts and polyps) – Other (Progressive Disease)”** under the system organ class (SOC) of the same name. Evidence that the death was a manifestation of underlying disease (e.g., radiological changes suggesting tumor growth or progression: clinical deterioration associated with a disease process) should be submitted.

Per NIH OBA Appendix M, should a patient die during the study or study follow-up, no matter what the cause, the study doctor will ask the patient's family for permission to perform an autopsy. If permission is granted, a copy of the autopsy report will be sent to the sponsor after all identifying information has been removed. An autopsy will help the researchers learn

more about the safety and efficacy of the treatment. Patients should advise their families about their wishes regarding autopsy.

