10.81 Reporting of Deaths

All deaths occurring through the 30-day follow-up period must be reported to Taiho Pharmacovigilance or designee **within 24 hours**.

1. Death due to disease progression:

Disease progression (radiologic or clinical) with the outcome of death will not be reported as an SAE. However, relevant signs, symptoms and complications of disease progression (radiologic or clinical) must be reported as an AE or SAE if it meets the serious criteria. It should be indicated that the signs, symptoms and complications are related to disease progression.

2. Death due to other causes:

Deaths due to reasons other than disease progression must be reported as an SAE.

Death is not an acceptable AE/SAE term. Death is an outcome of an SAE.

When reporting a death, the investigator will be required to identify which of the following best describes the category of death:

- Toxicity for study drugs
- Radiologic disease progression
- Clinical disease progression
- Other causes

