10.82 Disease Progression

How to report events related to non-fatal disease progression:

- a. Disease progression is not an acceptable AE term. In cases of non-fatal disease progression, the relevant signs, symptoms and complications should be reported as an AE unless they meet the serious criteria. If any of the signs, symptoms and complications meets any of the serious criteria, they should be reported as an SAE. In both cases it should be indicated whether the signs, symptoms and complications are related to disease progression.
- b. Radiologic disease progression without relevant signs, symptoms and complications will **not** be reported as an AE or SAE.

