16.42 Adverse Event Stopping Rules

The stopping rules specified below are based on the knowledge available at study development. We note that the Adverse Event Stopping Rule may be adjusted in the event of either (1) the study re-opening to accrual or (2) at any time during the conduct of the trial and in consideration of newly acquired information regarding the adverse event profile of the treatment(s) under investigation. The study team may choose to suspend accrual because of unexpected adverse event profiles that have not crossed the specified rule below.

Accrual will be temporarily suspended to this study if at any time we observe events considered at least possibly related to study treatment (i.e. an adverse event with attribute specified as “possible”, “probable”, or “definite”) that satisfy either of the following:

- If 3 or more patients in the first 10 treated patients (30% or higher after first 10 patients) experience at least one grade 4+ adverse event at least possibly related to the study treatment
- If one or more patients in the first 10 treated patients (20% or higher after first 10 patients) experience a grade 5 adverse event at least possibly related to the study treatment

We note that we will review Grade 4 and 5 adverse events deemed “unrelated” or “unlikely to be related”, to verify their attribution and to monitor the emergence of a previously unrecognized treatment-related adverse event.

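### Section 10.32 says an admission for signs of progression is not an SAE because no adverse event exists, while 10.82 and 10.41 make it one; the last bullet of 10.32 should be removed or narrowed

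*Combined protocol and SAP*

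**What the plan says.** **Non-fatal events.** Section 10.32 introduces a list with "The following hospitalizations are not considered to be SAEs because there is no" adverse event associated with them. The last item is "Hospitalization, or other serious outcomes for signs and symptoms of progression of the cancer". Section 10.82, on non-fatal progression, says of the relevant signs, symptoms and complications: "If any of the signs, symptoms and complications meets any of the serious criteria, they should be reported as an SAE". It also asks the site to indicate whether they relate to progression. Section 10.41 lists among the seriousness criteria "An adverse event that results in inpatient hospitalization or prolongation of existing hospitalization for" at least 24 hours. It requires SAEs to be reported to the sponsor whether or not they are considered related. The definitions in 10.0 make any untoward medical occurrence an adverse event, drug-related or not.

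**Deaths.** Section 10.52 asks for routine and expedited reporting regardless of causality. It states "Death due to progressive disease should be reported as" a Grade 5 neoplasm event with Progressive Disease as the specified term. Section 10.81, part of the supplier's additional instructions in 10.8, states "Disease progression (radiologic or clinical) with the outcome of death will not be reported as an SAE".

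**Where the records are used.** Section 10.622 sends Grade 3 and 4 adverse events to the case report form regardless of attribution. Section 10.6231 does the same for any death within 30 days of the last treatment. Section 16.324 tabulates the maximum grade for each type of event. In 16.42, "we will review Grade 4 and 5 adverse events deemed" unrelated or unlikely to be related, so that their attribution can be verified.

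**The concern.** The bullet in 10.32 goes further than waiving a fast reporting route. It says that the event is not an SAE and gives as the reason that there was no adverse event at all. A site that follows it has nothing to enter under 10.622, and a Grade 4 event that is never entered cannot be re-checked under 16.42.

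That matters here because tumor and drug can produce similar admissions. Appendix III lists cholangitis, biliary tract infection, sepsis and febrile neutropenia among serious reactions to FTD/TPI. In a patient with biliary cancer, a fever or a biliary infection could readily be put down to the tumor. The purpose of 16.42 is to have someone other than the treating site look at such judgments. As written, 10.32 lets the local judgment decide whether there is a record to look at.

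**Working it through.** No figure in the plan rests on this point, so the check is a comparison of the sections, followed by what can be said about size.

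1. **One admission, traced through the sections.** Take a Grade 4 event with a hospital stay of at least 24 hours that the site attributes to progression.
   - Definitions in 10.0: an adverse event, because cause does not matter.
   - 10.41: serious, because of the stay.
   - 10.82: an SAE, with its relation to progression noted.
   - 10.32, last bullet: not an SAE, because no adverse event exists.

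   Section 10.81 sides with 10.82. Even when progression is fatal, it wants the signs, symptoms and complications reported as an AE, or as an SAE if serious. No section gives an order of precedence.

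2. **Effect on the routine record.** Section 10.622 applies to adverse events. If the event is one, it is entered; if 10.32 is taken at its word, 10.622 has nothing to act on. The gap is limited. Terms listed in 10.61, such as abdominal pain, vomiting, anemia and neutrophil count, are graded at each evaluation anyway. Unlisted terms, such as cholangitis or sepsis, are the ones exposed.

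3. **Effect on safety monitoring.** The re-check in 16.42 covers Grades 4 and 5, so an omitted Grade 3 event affects only the table in 16.324. For Grade 4, accrual is suspended if 3 of the first 10 treated patients (30% or more thereafter) have a Grade 4 or higher event at least possibly related to treatment. One affected patient among the first 10 is 1/10 = 10 percentage points, or one of the three needed. The rule is affected only if the re-check would have changed the attribution to at least possibly related.

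4. **Is the overlap plausible?** Appendix III covers 769 patients with colorectal cancer on monotherapy. It gives febrile neutropenia as 18/769 = 2.3%, and cholangitis, biliary tract infection and sepsis as 1/769 = 0.1% each. These figures show that the drug can cause such events. They are not rates for this trial.

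5. **Deaths.** A progression death within 30 days of the last dose is expedited as Grade 5 under 10.52, entered as Grade 5 on the case report form under 10.6231, and notified to the supplier within 24 hours under 10.81. Section 10.81 removes only the SAE label. The conflict is therefore about SAE status and the form of the report. The death is recorded on either reading.

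**The case against.** **The event is captured anyway.** Section 10.32 is headed as exceptions to expedited reporting, and 10.622 and the definition in 10.0 govern routine capture. The 16.42 review depends on grade and not on SAE status. A careful site could read the bullet that way, and this keeps the problem modest. It does not remove it, because the bullet's stated reason is that no adverse event exists. The routine route works only if the site disregards that reason.

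**Misattribution can happen under any wording.** True. But an event recorded with a mistaken attribution can be re-checked, and an unrecorded one cannot.

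**Section 10.8 is a separate stream for the supplier.** Its heading supports this, and it is a sensible way to reconcile 10.52 with 10.81. The protocol does not say so, however. Sections 10.84 and 10.85, within 10.8, also direct what is captured on the case report form, though only for medication errors and overdose.

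Two stronger readings are tempting, and the documents do not support them:
- A reader might infer that the Grade 5 count swings from several events to none according to the section followed. Section 10.6231 puts any death within 30 days on the case report form as Grade 5 regardless of attribution.
- A reader might infer that 10.82 forbids the Grade 5 code, since it says "Disease progression is not an acceptable AE term". That sentence stands under a lead-in on non-fatal progression, so it does not govern the coding of deaths.

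**Conclusion.** The contradiction between the last bullet of 10.32 and 10.82, 10.41 and the definition in 10.0 is real and should be corrected. Its consequence is specific: a local judgment of progression could keep a Grade 3 or 4 event off the routine record, and a Grade 4 event out of the attribution re-check. This assumes that a site takes the bullet's rationale literally. How often that would happen cannot be estimated, because the documents give no rate of admission for progression.

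The conflict between 10.52 and 10.81 on progression deaths is secondary. It concerns the SAE label and which report carries it. The Grade 5 count on the case report form and the number of deaths do not change, and neither do overall survival, the primary endpoint or power. Section 16 plans no SAE tabulation, and the Grade 5 stopping rule counts only events at least possibly related to treatment. No efficacy conclusion is at risk.

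**What to change.** 1. Delete the last bullet of 10.32. Alternatively, limit it to an exemption from expedited reporting to the cancer center, and state that the event is still recorded as an AE or SAE according to grade and seriousness, with its relation to progression noted.
2. Add a sentence to 10.52 and 10.81 saying that 10.52 and 10.6231 govern the trial database and 10.81 governs the report to the supplier.

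No change to 16.324 is needed. It already tabulates by type of event, and 10.52 gives a progression death its own term. The cost is a wording amendment and a few more routine adverse event entries.
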